4.6.4 End of treatment visit

The End of Treatment Visit will take place when the participant completes his/her prescribed TB treatment regimen. This visit approximately will be held on month 6th or 7th for participants with DS TB category 1 therapy, on month 8th or 9th for participants with DS TB category 2 therapy, and between month 18th to 24th for those with MDR. However, the end of treatment visit might be different for some participants depend on their comorbidity or any other condition such as the new regimen for TB patient.

The following data and evaluations will be collected and performed:

- TB related symptoms
- Treatment compliance
- Comorbidities
- Weight

- Chest X-ray
- AFB (if available)
- Sputum culture (if available)
- Store whole blood (PAXgene, PBMCs, plasma)
- Store urine
- Store sputum and Mtb isolate (if available)
- Store saliva

4.6.5 6 Months Post-Treatment Visit

The final study visit will be conducted 6 months after the participants' prescribed TB treatment is completed. The data of TB related symptoms, weight, and chest X-Ray will be obtained by direct visit. If the participants unable to come for this visit, phone call should be made to obtain the data of TB related symptoms.

4.6.6 Study Disposition Status

Study disposition status will be completed with the Research Assistant when the participants considered as end of study. The final outcome of treatment will be determined.

Participants followed until 6 months post treatment visit will be considered as completing the study procedure and end of study. The rest of the participants will be considered as end of study at the following time point:

- 1. Participant withdraws consent.
- 2. Participant who is unable to provide enough sputum at baseline/enrollment visit for the examinations of AFB, Gene Xpert, and culture.
- **3.** Participant is no longer treated as TB patients.
- **4.** Participant has treatment interruption of two months or longer after she/he starts TB treatment.
- 5. Participant died.
- **6.** Participant transfers to other health facility for their TB treatment where follow up/ evaluation is no longer possible.
- 7. Based on investigator discretion.
- **8.** Participant who cannot be reached to complete the 6 month post treatment by phone or direct visit.
- **9.** Termination of study.

At this visit the final outcome **of treatment** status will be determined.

All study procedures will be outlined in Appendix A

4.6.7 TB Management

Participants who are not diagnosed with MDR-TB will be managed according

to the Indonesia MoH 2011 national TB guidelines, and those diagnosed as MDR-TB cases will be managed in accordance to Indonesia Programmatic Management of Drug- Resistant TB (PMDT) 2013. Other drug resistant TB cases will be managed in accordance to each site clinician decision. Treatment for tuberculosis is provided free of charge by the National TB Program.

4.6.8 Handling of Samples

Sputum specimen will be collected at special booth at each site. Culture and DST will be performed at laboratories which capable to perform culture, bacterial identification and DST according to international standard, and have passed Quality Assurance by TB supranational laboratory. All sputum specimen and Mtb isolate will be processed in biosafety cabinet level 2. Blood and urine specimen will be collected in Pathology Clinic at each site. Blood and urine specimen collection and handling will be up to each hospital and/or Pathology Clinic laboratory safety procedure at each site.

Transport of biological samples

As the transmission of TB can occur through contact with sputum specimens, contact and respiratory precautions will be employed by all personnel involved with sputum collecting, shipping and handling for this study.

Archived Biological Materials

Samples collected under this protocol may be used to study TB and related conditions such as spoligotyping. Participants must be willing to allow storage of sputum, Mtb isolate, whole blood (PAXgene blood, plasma, PBMC), and urine on baseline, month 1, month 2, and end of treatment visit, and saliva on baseline and end of treatment visit for use in future studies (for example, host response, spoligotyping, and genetic tests). Serum and whole blood for DNA are collected on baseline visit only.

All samples will be stored at the NIHRD, Mtb isolate, plasma, saliva and urine will also be stored at each site. Samples will be coded with a unique identifier that does not contain any information capable of linking the sample to the study participants. A code that links the unique identifier with the study sample will be kept on a locked file cabinet in a secured room. Only authorized personnel will have access to the code. Only investigators will have access to the samples. **All samples will be logged and tracked using INA-RESPOND system.**

Some of the specimens collected under this protocol will be stored for

repository. The used and destruction of the archived specimens in the future, will be determined per INA-RESPOND SOP of Specimen Ownership, Access, and Use (see appendix D).

Additional testing on study samples

Based on the clinical presentation and laboratory data the researchers will determine further testing to be done on samples. This testing could be performed for: a) existing diagnostic methods that may not have been accessible at the time of the collection of samples, b) research tests to identify and/or confirm etiologic agents, c) to study immune markers that might enable better management or prediction of outcomes for patients, d) to be used to study pathogenicity, and e) genetic testing.

IRB approval must be sought prior to any sharing of samples and/or data. Any clinical information shared about the sample would similarly require prior IRB approval. At the completion of the protocol (termination), samples and data will either be destroyed, or after IRB approval, transferred to another existing protocol. Reporting the Loss or Destruction of Samples/Specimens/Data to the IRB

Any loss or unanticipated destruction of samples or data (for example, due to freezer malfunction) that compromises the scientific integrity of the data collected for the study will be reported to the IRB.

Additionally, participants may decide at any point not to have their samples stored. In this case, the principal investigator will destroy all known remaining samples and report what was done to both the participant and to the IRB.

4.7 Data Management and Analysis

4.7.1 Data Management

Data which are collected under this protocol may be used to study TB and related conditions. Participant will be coded with a unique identifier that does not contain any information capable of linking the data to the study participants. A code that links the unique identifier with the study participants will be kept in a locked file cabinet in a secure room. Only authorized personnel will have access to the code and the data. Data will be keyed and tracked using the OpenClinica.

Data will be periodically sent to the central data management center. Site and national data will be analyzed by all investigators.

4.7.2 Analysis

This is an observational study to describe rates of MDR TB amongst new and previously treated TB cases in Indonesia. Risk factors for MDR will be evaluated as a secondary objective. Additional secondary objectives include a description of treatment outcomes (cure, failure, death, completed treatment) and evaluation of associated risk factors for poor outcome, comparison of diagnostic accuracy of AFB and Xpert MTB/RIF (relative to culture) and an estimation of Xpert MTB/RIF Rif susceptibility testing sensitivity and specificity relative to standard DST. Research objectives will be analyzed as described below.

Primary objective

 To estimate the rate of MDR-TB amongst new and retreated TB cases. Proportions of MDR will be estimated, along with exact 95% confidence intervals based on a binomial distribution. Case definitions of MDR, new and previously treated TB are provided in Appendix B.

Secondary objective

- To estimate treatment outcomes (cured, failed, died, treatment completion, and lost to follow up) according to susceptibility pattern. Proportions of participants within each category will be estimated along with confidence intervals. Definitions of treatment outcomes are provided in appendix B.
- 2) To evaluate risk/protective factors for treatment success (cured or completed treatment vs failed or died or loss to follow up). These factors include: demographics (age, sex), TB contact history, smoking habit, treatment seeking behavior, co-morbidities (HIV, DM), primary drug resistance, symptoms, no cavity in the lung, nutritional status, treatment regimens, compliance, numbers of bacteria and TB strains (e.g., Beijing). Logistic regression models will be used to describe associations of treatment success with these factors.
- 3) To evaluate risk/protective factors for treatment interruption (loss to follow up vs other treatment outcome). These factors include: demographics (age, sex), TB contact history, smoking habit, treatment seeking behavior, co-morbidities (HIV, DM, and other comorbidities), primary drug resistance, symptoms, cavity in the lung, nutritional status, treatment regimens, compliance, numbers of bacteria and TB strains (e.g., Beijing). Logistic regression models will be used to evaluate associations of treatment interruption with these risk factors.
- To compare clinically defined TB against laboratory confirmed TB. Accuracy will be estimated along with 97.5% confidence intervals.
- 5) To compare the sensitivity and specificity of AFB and Xpert MTB/RIF relative

to culture result. Sensitivity and specificity will be estimated along with 97.5% confidence intervals. McNemar's statistic will test whether the sensitivity and specificity differ between AFB and Xpert MTB/RIF.

6) To estimate sensitivity and specificity of Rif susceptibility results in Xpert MTB/RIF against result in DST as gold standard along with 97.5% confidence intervals.

More specific plans for these analyses will be developed prior to the start of enrollment, and the plans may be adjusted during the course of the study.

Interim Analyses

Amongst presumptive new TB cases, we estimate that 25% will have confirmed TB, while amongst presumptive previously treated cases, we estimate that 70% will have confirmed TB. In order to ensure adequate numbers of TB cases, the accuracy of these estimates will be evaluated at 6 and 12 months after the study commences. Because of the expected two months waiting period for culture results, earlier looks at the data may not be informative.

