4.2 Sites and Duration

This study will be conducted at hospitals in the INA-RESPOND network:

- 1. Persahabatan hospital, Jakarta
- 2. [name]. Sulianti Saroso Infectious Diseases hospital, Jakarta
- 3. [name] hospital, Bandung
- 4. [name] hospital, Semarang
- 5. [name] hospital, Surabaya
- 6. Sanglah hospital, Bali

- 7. [name] hospital, Yogyakarta
- 8. [name] hospital, Makassar
- 9. Gatot Subroto Army hospital, Jakarta
- 10. H. Adam Malik Hospital, Medan
- Patients suspected of having pulmonary TB
 - Cough ≥ 2 weeks
 - At least 1 other TB clinical symptoms (fever, unexplained weight loss, loss of appetite, hemoptysis, shortness of breath, chest pain, night sweats, fatigue)
- Suggestive TB on chest x-ray based on pulmonologist or internist consultant of pulmonology opinion
- Age ≥18 years old
- Participants (with or without TB treatment history) are screened whether they meet the following criteria:
 - Willing to be treated or evaluated at study site
 - Willing to have specimens stored for use in future studies
 - Patient denies having TB treatment for maximum 7 days in the last 1 month
 - Pregnancy or any serious condition include, but are not limited to, liver disease, chronic kidney disease, and psychiatric illness, that might interfere with study compliance

[figure not shown]

Figure 1. The Study Plan

The Study will enroll eligible participants for a period of up to 2 years. Participants will be followed up until 6 months' post treatment. For drug susceptible TB, this will be approximately 12 months after enrollment/treatment start, but it may be longer if they have drug resistant TB or require longer treatment regimen for other reasons (e.g. Category 2 treatment, diabetes, etc). For those participants, the study will follow them for maximum 30 months after enrollment/treatment start. Stored specimens will be investigated during the study and/or after study completion.

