Failed	Attending TB team report	 Treatment terminated or need for permanent regimen change at least two anti-TB drugs because of: Lack of conversion at the end of intensive phase; or Bacteriologocial reversion in the continuation phase after conversion to negative; or Evidence of additional acquired resistance to fluoroquinolones or second-line injectable drugs; or Adverse drug reactions
Died	Attending TB team report	Died for any reason during course of treatment
Loss to follow up	Attending TB team report	Treatment was interrupted for two consecutive months or more.
Not evaluated	Attending TB team report	No treatment outcome is assigned. This include cases 'transferred out' to another treatment unit as well as cases for whom the treatment outcome is unknown.
Treatment success	Attending TB team report	The sum of Cured and completed treatment.

Demographics						
Age	Patient report	Last birthday				
Sex	Patient report	male and female				
Patient's history						
TB close contact	Patient report	Living in a same house with person who has TB				
Smoking habit	Patient report	Smoking status of participants				
Treatment seeking behavior	Patient report	History of health facility that been visited for treating these TB symptoms				
Co Morbidities						
HIV	Clinical and laboratory evaluation support HIV evidence	Positive result of HIV test				
Diabetes mellitus	Clinical and laboratory evaluation support diabetes evidence glucose test according to site SoC	Positive result of diabetes				
Symptoms	Patient report	Presence of TB symptoms from previous visit to current visit				
Nutritional status	BMI calculation based on data of Height and weight	< 18.5				
Treatment regiment	Source documents	Regiment of anti TB drugs given to the patients according to SoC				
Compliance	Patient report or blister count	Percentage of scheduled medication minus any medication left in the blister or based on patient report				

REFERENCES

1. World Health Organization W. Global Tuberculosis Control, Surveillance, Planning and Financing. Geneve: 2006.

2. World Health Organization W. Global Tuberculosis Control 2010. Geneve: 2010.

3. World Health Organization W. Global Tuberculosis Report 2016. Geneva: World Health Organization; 2016.

4. Departemen Kesehatan Republik Indonesia. Pedoman Nasional Penanggulangan Tuberkulosis. Jakarta2007.

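### The factor lists for treatment success and interruption include regimen but omit new versus previously treated status, leaving regimen associations open to confounding by treatment history and resistance

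*Combined protocol and SAP*

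**What the plan says.** Item 2 of the secondary analyses in 4.7.2 compares cured or completed treatment with failure, death or loss to follow-up. Its factors, after demographics, contact history, smoking, treatment seeking and co-morbidities, are "primary drug resistance, symptoms, no cavity in the lung, nutritional status, treatment regimens, compliance, numbers of bacteria and TB strains (e.g., Beijing"). The method is one sentence: "Logistic regression models will be used to describe associations of treatment success with these factors". Item 3 compares loss to follow-up with the other outcomes, using "primary drug resistance, symptoms, cavity in the lung, nutritional status, treatment regimens, compliance, numbers of bacteria and TB strains (e.g., Beijing") and the sentence "Logistic regression models will be used to evaluate associations of treatment interruption with these risk factors". New versus previously treated status appears in neither list, nor among the 13 factors in 3.3. Section 3.3 does name both primary and secondary resistance, where 4.7.2 names only primary.

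On how regimen is determined, 4.6.7 says that "those diagnosed as MDR-TB cases will be managed in accordance to Indonesia Programmatic Management of Drug- Resistant TB (PMDT) 2013", that participants without MDR-TB follow the national guideline, and that other resistant cases are left to the site clinician. Section 4.6.4 puts the end of treatment "on month 8th or 9th for participants with DS TB category 2 therapy, and between month 18th to 24th for those with MDR", against month 6 or 7 for Category 1. Section 4.2 mentions participants who "require longer treatment regimen for other reasons (e.g. Category 2 treatment, diabetes, etc").

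Appendix B defines regimen as "Regiment of anti TB drugs given to the patients according to SoC", with no time point, and 4.6.3 has it recorded at every study visit. Appendix B also defines new and previously treated cases, and Appendix A collects TB history at baseline.

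**The concern.** A regimen chosen because of a patient's resistance or history carries the prognosis of that patient. If the model omits the reason for the choice, the regimen term takes up its effect. Here the omitted variable is the one on which the study recruits two separate cohorts of 250.

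Resistance is only partly covered. In its usual meaning (Appendix B does not define it), primary resistance is resistance in patients not previously treated, so the 4.7.2 list would leave most MDR patients uncoded.

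Timing adds a second problem. With regimen recorded at every visit and no reference time, a regimen changed during treatment may be the value analysed. In the MDR definitions of Appendix B, a permanent change of at least two drugs for certain reasons is itself failure. A regimen variable that reflects such a change would partly restate the outcome.

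At stake is a secondary result that could show a regimen as harmful or protective without any such effect, while a cohort-defining factor goes unreported. Section 2.3 says the results may inform the national programme's strategy for treatment. The primary MDR proportions are unaffected.

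**Working it through.** **Inputs from the documents.** 250 confirmed cases per cohort; confirmation rates 25% and 70%; MDR rates 1.9% (new) and 12% (previously treated), all from 4.4. The background gives 2.9%/16% and 1.8%/17.1%.

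**Step 1, the plan's own figure.** 250/0.25 = 1,000 and 250/0.70 = 357, total 1,357. This agrees with 4.4.

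**Step 2, link between MDR regimen and history.** Expected MDR cases are 250 × 0.019 = 4.75 new and 250 × 0.12 = 30 previously treated. The previously treated share is 30/34.75 = 86%. The odds ratio of MDR for history is (0.12/0.88)/(0.019/0.981) = 7.0. The background rates give 40/47.25 = 85% and 42.75/47.25 = 90%. This link needs no outside rule.

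**Step 3, what the 4.7.2 resistance factor covers.** On the usual meaning, primary resistance codes about 5 of 35 MDR cases and leaves about 30 uncoded. Adding secondary resistance, as in 3.3, codes those 30. It does not separate the roughly 220 previously treated non-MDR participants (250 × 0.88) from the 245 new ones (250 × 0.98, rounding the new rate to 2%).

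**Step 4, illustration for Category 1 versus Category 2.** The assumptions, none of them in the documents, are: no regimen effect; success 85% in new non-MDR cases and 80%, 75% or 70% in previously treated ones; and the allocations in the table. The odds ratio (OR) comes from expected 2×2 counts, SE(log OR) is the square root of the sum of reciprocal counts, and the rejection probability is for a two-sided 5% Wald test.

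Full allocation at 75%: OR = (165/55)/(208.25/36.75) = 0.53; SE = 0.237; z = −0.636/0.237 = −2.68; rejection Φ(2.68 − 1.96) = 76%.

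Allocation 90%/5% at 75%: Category 2 has 198 + 12.25 = 210.25 participants with 198 × 0.75 + 12.25 × 0.85 = 158.91 successes. Category 1 has 22 + 232.75 = 254.75 with 214.34 successes. OR = (158.91/51.34)/(214.34/40.41) = 0.58.

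| Category 2 share, previously treated / new | 80% | 75% | 70% |
|---|---|---|---|
| 100% / 0% | 0.71 (29%) | 0.53 (76%) | 0.41 (97%) |
| 90% / 5% | 0.74 (23%) | 0.58 (63%) | 0.47 (91%) |
| 50% / 5% | 0.82 (11%) | 0.71 (28%) | 0.62 (51%) |
| 30% / 5% | 0.86 (8%) | 0.77 (15%) | 0.69 (25%) |

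Cells show the apparent odds ratio for success (rejection probability). Columns are assumed success in previously treated cases.

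**Step 5, does adjustment remove it?** Expected-count logistic fits with three regimen levels, no true effect of Category 2, and assumed success of 85% (new, drug-susceptible), 65% (previously treated, drug-susceptible), 55% (new MDR) and 50% (previously treated MDR):

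- Allocation 60%/5%: Category 2 OR 0.52 with regimen only, 0.52 after adding primary resistance, 0.97 (95% CI 0.57 to 1.64) with history instead.
- Allocation 100%/0%: 0.33, 0.33, then 0.40 (0.05 to 2.94). Here the history term rests on about 5 new MDR patients, so history does not recover the null.
- If the MDR regimen coincides with MDR status, a model holding both is not estimable.

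History helps where regimens overlap across history. Where they do not, no covariate list identifies a regimen effect.

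**The case against.** The strongest reply is that the mechanism within drug-susceptible disease lies outside the documents. They show that Category 2 exists and lasts longer, but not who receives it. They give no success rate by treatment history, and the background's list of factors linked to success does not include it. With full allocation, the Step 4 odds ratio is simply the ratio of two assumed success odds, and high rejection rates need both a wide gap and near-complete allocation. That stands, so those figures are illustrative only.

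It is also fair that the plan claims only associations, that its lists are open-ended, that diabetes is already a listed factor, and that outcomes are to be reported by susceptibility pattern. Section 4.7.2 also defers detail to plans to be made before enrolment. These points lower the certainty but do not supply the missing variable. The deferral does not correct lists already written, and a cohort-defining covariate should be fixed in advance.

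Two stronger readings are tempting. A reader might infer that the regimen association simply is confounding by indication; the documents support only that it may be confounded, by an unknown amount. A reader might also infer one joint model over all treated participants; the text refers to models in the plural and states neither adjustment nor population. If the analyses were univariable, the confounding would be wholly uncontrolled.

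**Conclusion.** The point holds in limited form. Regimen is listed, treatment history is not, and regimen follows MDR diagnosis. On the protocol's rates 85% to 90% of MDR cases are previously treated (86% at the design rates), so regimen associations from these lists are open to confounding by history and resistance. The primary-resistance factor in 4.7.2 does not remove it.

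The size cannot be determined. Under the assumed allocations and success rates, a regimen with no effect shows odds ratios for success from 0.33 to 0.86 when history is left out. That range gives direction and plausibility, not an estimate. The 86% assumes that the planned 250 + 250 confirmed cases and the design MDR rates are realised. The statement about primary resistance assumes its usual meaning.

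This is a cheap improvement to secondary analyses, held with medium confidence.

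**What to change.** In 4.7.2, items 2 and 3 (and 3.3 to match):

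1. Add new versus previously treated status, as defined in Appendix B, as a covariate.
2. Reconcile the resistance factor in 4.7.2 with the wider one in 3.3, and use full resistance status.
3. Analyse MDR-TB and non-MDR TB separately, since Appendix B defines their outcomes differently. Keep the MDR analysis mainly descriptive.
4. Define regimen as the one at treatment start. Report outcomes by regimen descriptively within history and MDR strata, and do not interpret a regimen coefficient where the strata do not overlap.

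Item 1 alone is not enough, as Step 5 shows. The cost is analysis wording; no new data are needed. The downside is that about 35 MDR cases allow little modelling, and some regimen comparisons will have no adjusted estimate.
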